9.2.1. Reactogenicity Assessments: eDiaries

Temperature (degrees celsius or fahrenheit to one decimal point), 7 systemic reactogenicity symptoms and 2 local reactions were collected pre-dose and once daily for the 7 days following IP administration via a reactogenicity eDiary, see Protocol Appendix 1. Symptoms were reported by the subject, at 5 levels of intensity (0=None, 1=Mild, 2=Moderate, 3=Severe, 4= Medically attended).

Investigators (or designee) were required to review the reactogenicity eDiary data daily as part of the ongoing safety review. The site was to be notified if a subject had entered a Grade 3/4 severity for a symptom. The site was then required to contact the subject to confirm the scoring and determine whether subject should attend the clinic for further follow-up. The Investigator was required to evaluate the symptoms and assess whether they agree with the grading of 3 or higher. Regardless of the PI assessment, the diary entries were not to be changed, and the Investigators were to either verify the patient-recorded score or note a discrepancy in the source documentation. If any discrepancies or changes in reporting were noted at review, both uncorrected and corrected data were to be recorded and both sets of symptom scores transferred from the eDiary vendor. Corrected eDiary data will be summarized in the CSR. Original data entries as recorded by the patient and/or where these differ from final reports will be given in an appendix to the CSR. Missing eDiary data will be reported as missing; no symptom values were to be imputed.

Daily temperatures and worst (maximum) temperature over the 7 days experienced by each subject will be summarized using descriptive statistics.

Worst symptom severity experienced over the 7 days and the number of days with any grade of symptom (score > 0) will be summarized using frequencies and percentages.

These summaries will use the IPEVAL set.

Symptoms tables include both local reactions and systemic symptoms.

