2.2. Endpoints

2.2.1. Primary Endpoints

The primary endpoints are:

- The number and percentage of study participants who experience solicited local and systemic reactions during the 7 days after administration of investigational M2SR vaccine or placebo, as recorded through subject electronic diary (eDiary).
- The number and percentage of study participants who experience unsolicited AEs during the 28 days after administration of investigational M2SR vaccine or placebo and prior to administration of licensed QIV.
- The number and percentage of study participants who experience SAEs from the time of informed consent through 28 days after receipt of QIV.

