6.2.4. Electronic Diary

Subjects will be required to complete a reactogenicity eDiary through an application installed on the subject's own personal device. Site will train the subject on the application during Visit 01. All subjects will be asked to monitor and record local reactions, systemic events including temperature, and antipyretic medication usage for 7 days following administration of IP. The reactogenicity eDiary allows recording of these assessments only within a fixed time window, thus providing the accurate representation of the subject's experience at that time. Data on local reactions and systemic events reported in the reactogenicity eDiary will be transferred electronically to a third-party vendor, where they will be available for review by Investigators via an internet-based portal or reports extracted from the portal.

At specified intervals, these data will be retrieved electronically to the Sponsor for analysis and reporting. These data will be reported in the database but do not need to be reported separately by the Investigator in the eCRF as AEs.

Investigators (or designee) will be required to review the reactogenicity eDiary data daily as part of the ongoing safety review. The site will be notified if a subject has missed a diary entry. The eDiary application will remind the subject to populate the diary and will notify the site of the event. If a subject continues to be delinquent the site will contact the subject by phone and will document any missed entries as a protocol deviation. The site will also be notified if a subject has entered a Grade 3 or Grade 4 severity for a symptom. The site must contact the subject to confirm the scoring and determine whether subject should attend the clinic for further follow-up. The Investigator is required to evaluate the symptoms and assess whether they agree with the grading of 3 or higher. Regardless of the PI assessment, the diary entry will not be changed, and the Investigator will verify the score or note a discrepancy in the source.

The Investigator or designee must obtain stop dates from the subject for any ongoing local reactions, systemic events, or use of antipyretic medication on the last day that the reactogenicity eDiary was completed. The stop dates should be documented in the source documents and the information entered in the eCRF.

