6.2.4.2. Systemic Events

During the reactogenicity reporting periods, subjects will be asked to assess headache, fatigue, myalgia, and illness. For the post-IP period, this will include recording the symptoms in the reactogenicity eDiary. The symptoms will be assessed by the subject as none, mild, moderate, severe or medically attended – emergency room visit or hospitalization was required according to the grading scale in Appendix 1.

If a Grade 3 or Grade 4 systemic event is reported in the reactogenicity eDiary after administration of IP, a telephone contact should occur to ascertain further details and determine whether a site visit is clinically indicated. If a systemic reaction persists beyond the end of the reactogenicity period following vaccine administration, the subject will be requested to report that information. The Investigator will enter this additional information as an AE in the eCRF. If a Grade 3 systemic reaction is reported after QIV administration (Visit 04) and prior to Visit 05, the site should ascertain whether a site visit is clinically indicated. If a Grade 3 or Grade 4 respiratory event (for example cough or wheezing) has been confirmed by the site, the subject should attend the clinic to provide a nasal swab that is tested as soon as possible for the full panel of respiratory agents.

Only an Investigator or medically qualified person is able to classify a subject's systemic event as Grade 4. If a participant experiences a confirmed Grade 4 systemic event, the Investigator must immediately notify the Sponsor.

Solicited systemic events following the IP dose include:

- Fever
- Chills
- Muscle aches
- Decreased activity
- Decreased appetite
- Headache
- Cough
- Sore throat

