6.2.4.3. Fever

In order to record information on fever, a digital thermometer will be provided to subjects with instructions on how to measure oral temperature at home. Temperature will be collected in the reactogenicity eDiary in the evening daily during the reactogenicity eDiary reporting period. It will also be collected at any time during the reactogenicity periods, whether during eDiary data collection (post-IP) or post-QIV interval, when fever is suspected. Fever is defined as an oral temperature of ≥38.0°C (100.4°F). The highest temperature for each day will be recorded in the reactogenicity eDiary. Temperature will be measured and recorded to 1 decimal place and then categorized during PI analysis according to the scale shown in Appendix 1.

If a fever of $\geq 39.0^{\circ}$ C (102.1°F) is reported in the reactogenicity eDiary, a telephone contact should occur to ascertain further details and determine whether a site visit is clinically indicated. Subjects should be instructed that if they record a fever of $\geq 39.0^{\circ}$ C post-administration of QIV, they should contact the site as soon as possible. Only an Investigator or medically qualified person is able to confirm a participant's fever as $\geq 40.0^{\circ}$ C ($\geq 104.0^{\circ}$ F). If a participant experiences a confirmed fever $\geq 40.0^{\circ}$ C ($\geq 104.0^{\circ}$ F), the Investigator must immediately notify the Sponsor.

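### SAP 9.2.1 does not fully deliver the primary solicited-reaction endpoint: it plans no count of subjects with diary fever, and its main tables use corrected diary data that are not defined.

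*SAP*

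**What the plan says.** **Endpoint.** Protocol 2.2.1 lists as a primary endpoint "The number and percentage of study participants who experience solicited local and systemic reactions during the 7 days after administration", with the subject's own eDiary named as the data source.

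**Fever.** Protocol 6.2.4.2 puts fever first among the solicited systemic events. Protocol 6.2.4.3 sets the threshold at an oral temperature of 38.0°C and says that temperature is recorded and "then categorized during PI analysis according to the scale shown in Appendix 1". Appendix 1 asks for a temperature to one decimal but holds no temperature categories; the fever grades are in Appendix 2. For analysis, SAP 9.2.1 says: "Daily temperatures and worst (maximum) temperature over the 7 days experienced by each subject will be summarized using descriptive statistics". Frequencies and percentages are planned for worst symptom severity and for days with a symptom score above 0.

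**Corrected entries.** Protocol 6.2.4 states: "Regardless of the PI assessment, the diary entry will not be changed". The investigator either verifies the score or notes a discrepancy in the source. SAP 9.2.1 repeats that rule. It then says that where discrepancies or changes were noted at review, an uncorrected and a corrected version were both kept and transferred, and that "Corrected eDiary data will be summarized in the CSR". The subject's original entries go to a CSR appendix. SAP section 12 adds that diary collection and transfer were troublesome at first and that the vendor corrected the transfers.

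**The concern.** Solicited reactions in the first 7 days are a primary safety result, in what Protocol 1.4 describes as the first study of this vaccine in an older population. A reader of the report will want two simple things from the diary: how many subjects in each arm had a fever, and how many rated a reaction severe.

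The SAP does not plan the first as a count. For the second, the main table rests on a version of the data whose origin is not stated. Repairing a faulty transfer restores what the subject entered. Replacing the subject's score with a site's view changes the quantity that Protocol 2.2.1 defines. The SAP uses one word for both.

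**Working it through.** The only operating figure in the documents is in Protocol 1.4: a better than 95% chance of seeing an AE of 20% prevalence in 15 subjects. It reproduces, 1 − 0.8^15 = 0.965, but does not bear on this point. The check is mainly of text against text, with arithmetic on assumed values to show scale.

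**1. Which diary items get a count?**

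- Protocol 6.2.4.2 lists 8 solicited systemic events: fever, chills, muscle aches, decreased activity, decreased appetite, headache, cough, sore throat.
- SAP 9.2.1 counts 7 systemic symptoms and 2 local reactions, scored 0 to 4, and names temperature separately.
- 8 − 7 = 1. The item outside the scored set is fever. Frequencies and percentages attach to the scored items, so fever is the one solicited event with no n (%).

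**2. Does another planned output supply it?**

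- SAP 9.4 plans shift tables of worst grade that include fever. They stand in the vital-signs section and run from IP administration to QIV Day 29. Scheduled clinic temperatures (Protocol Tables 2 and 3) fall on Day 1, Day 8 ±1, Day 29 ±3 and the two QIV visits. A fever that began and ended between Day 1 and Day 8 could be missed, and one after QIV would be included.
- SAP 9.2 lets a diary symptom become an AE at the investigator's discretion, with no reconciliation between diary and AE records. AE tables are not a diary count.
- Protocol 8.3.2 promises diary symptoms by time point, worst occurrence and days with symptoms, but gives no fever row.

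**3. What do descriptive statistics show?** Arm size is 80 active (SAP 1.1.1). Assumptions, not from the documents: 7-day maximum of 38.5°C in a febrile subject and 36.9°C in any other. Mean maximum = [(80 − k) × 36.9 + k × 38.5] / 80.

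| Febrile k of 80 | Rate | Mean maximum | Median | Group maximum |
|---|---|---|---|---|
| 0 | 0% | 36.90°C | 36.9°C | 36.9°C |
| 4 | 5% | 36.98°C | 36.9°C | 38.5°C |
| 8 | 10% | 37.06°C | 36.9°C | 38.5°C |
| 16 | 20% | 37.22°C | 36.9°C | 38.5°C |

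The group maximum shows that at least one fever occurred, not how many. The median does not move. Between 5% and 20% the mean moves by 37.22 − 36.98 = 0.24°C.

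**4. Which way could re-scoring move the severe count?** Under Protocol 6.2.4 and SAP 9.2.1 all diary data are reviewed daily, but the site alert, the subject contact and the investigator's agreement check apply to Grade 3/4 entries. A change made at that step starts from Grade 3 or 4, so it leaves the Grade 3-or-higher count as it is or lowers it. A change arising from the general daily review could go either way.

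Illustration, with assumed rates, from 8/80 = 10% entered at Grade 3 or higher:

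- 25% lowered, none raised: 6/80 = 7.5%.
- 50% lowered, none raised: 4/80 = 5.0%.
- None lowered, 1% of the other 72 raised: 8.72/80 = 10.9%.
- None lowered, 2% of the other 72 raised: 9.44/80 = 11.8%.

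The documents give no correction rate, so neither the size nor the net direction is known.

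**The case against.** A reader might infer that investigators overwrite scores, that only Grade 3/4 entries are reviewed, that fever is reduced to a mean, and that severity and fever are therefore understated. The documents do not support that reading.

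- **Who corrects.** No passage has the investigator overwrite a score. The role is to verify it or note a discrepancy. SAP section 12 attributes at least some corrections to vendor repair of transfers, and a change noted on contact could be the subject's own correction of a slip. The ambiguity remains, because the SAP 9.2.1 sentence creating corrected data speaks of discrepancies noted at review and follows directly on the agreement check.
- **What is reviewed.** All entries are, daily. Only mandatory confirmation is confined to Grade 3/4.
- **What is summarized for temperature.** Each subject's maximum is summarized as well as the daily values. Where the SAP lists its summary statistics (section 5, for baseline), they include the maximum, so the occurrence of fever would probably be visible. The number of subjects with fever would not.
- **What the endpoint counts.** Protocol 2.2.1 sets no severity threshold. Re-scoring 3 to 2 leaves the count of subjects with a reaction unchanged; only a change to 0 would alter it. The effect falls on the worst-severity display.
- **Nothing is hidden.** Both versions are kept and the originals are reported in an appendix. The question is which version the main table shows.
- **Grade 4.** Protocol 6.2.4.2 reserves the Grade 4 classification of systemic events to an investigator or medically qualified person, and Appendix 2 requires Grade 4 local scores to be confirmed. A table of subject entries would include Grade 4 scores without that confirmation. This is a real drawback of the remedy.

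These points limit the claim about bias. They do not supply the missing fever count or a definition of corrected data.

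**Conclusion.** Both parts hold, with different weight, and the sponsor should act on them.

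The fever gap is plain from the text. One listed solicited event is not planned in the form the primary endpoint requires, and no other table fills the gap. The temperatures above are assumed and serve only to show that a fourfold difference in fever rate can sit behind a small shift in the mean and an identical maximum.

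The corrected-data point is smaller. SAP 9.2.1 rules out changes to entries and then tabulates corrected ones without saying what a correction is. The SAP's precedence over the protocol (SAP section 1) does not settle this, because the tension lies within one SAP section. Lowering of the Grade 3-or-higher count follows only if clinical re-scoring at the confirmation step is part of the corrected data, which the documents neither state nor exclude. If every correction was a transfer repair, the plan already matches most of the remedy and needs only to say so. Understatement is a possibility to be closed off, not a finding.

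**What to change.** 1. **Fever rows.** In SAP 9.2.1 add, by arm, n (%) of subjects with a maximum 7-day eDiary temperature of 38.0°C or above, overall and by Protocol Appendix 2 grade. Keep the descriptive statistics. Reconcile the Protocol 6.2.4.3 reference to Appendix 1 for the fever scale with Appendix 2, where the grades stand.
2. **Define corrected.** State who may correct a diary record and on what grounds, and separate technical or transfer repair from a score changed or disputed at review.
3. **Main and supportive tables.** Base the main tables on subject-entered scores repaired only for documented technical or transfer faults. Put scores changed or disputed at review in an adjacent supportive table, not only in an appendix listing.
4. **Grade 4.** Footnote Grade 4 entries that an investigator has not confirmed, and reconcile the confirmation passages (Protocol 6.2.4.2 and Appendix 2) with this presentation.

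The cost is SAP wording and a few rows of output. No new data are needed, since temperatures are in the diary and both score versions are already transferred. The downside is small: some genuine entry errors and some unconfirmed Grade 4 entries will appear in the main table, where the footnote and the supportive table explain them.

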4. SELECTION OF STUDY POPULATION

4.1. Subject Inclusion Criteria

Subjects must meet all of the following criteria to be eligible for study participation:

- 1. Subjects must be willing and able to provide written informed consent.
- 2. Cohort 1: age 50-64 years at time of consent; Cohorts 2 and 3: age 65-85 years at time of consent.
- 3. Subjects must be willing to adhere to the requirements of the study and willing and able to communicate with the Investigator and understand the requirements of the study.
- 4. Healthy adults and those with stable chronic conditions as determined by medical history, physical examination, vital signs, clinical safety laboratory examinations and clinical judgment of the Investigator to be eligible for study inclusion.
- 5. Negative test (urine) for drugs of abuse at screening. Subjects who are on stable (6 months or longer) medications prescribed by their physician which result in a positive screen for that substance are allowed at the discretion of the Investigator if there is no anticipated interference with study safety assessments.
- 6. Non-smoker (defined as no use of tobacco products and no use of inhaled non-tobacco products in the past 30 days prior to Study Day 1; nicotine patches and gum are allowed). Subject must also agree to restrict the use of these products until 7 days after last vaccine administration.
- 7. Women of child-bearing potential must agree to abstain from sexual intercourse or to correctly use an acceptable method of contraception, as described below, from 30 days prior to vaccination until 30 days after the last study vaccination.
- 8. Childbearing potential is defined by the occurrence of menses within the past year, and not sterilized via tubal ligation, bilateral oophorectomy, hysterectomy, or successful Essure® placement (permanent, non-surgical, non-hormonal sterilization) with documented radiological confirmation test at least 90 days after the procedure and still menstruating.

Acceptable methods of contraception for female study participants include:

- non-male sexual relationships,
- abstinence from sexual intercourse with a male partner,
- monogamous relationship with a vasectomized partner,
- and correct use of
 - o male condoms with the use of applied spermicide,
 - o intrauterine devices,
 - o NuvaRing®,
 - o and licensed hormonal methods such as implants, injectables, contraceptive patches or oral contraceptives ("the pill").

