- 7 Specifically includes the nares (including edema), throat, and lungs (including evaluation for wheezing) up to and including Day 29. A targeted physical examination may be performed on other body systems if indicated based on review of interim medical history or subject symptoms as observed by site or by PI.
- 8 Dispense on day of dose then ongoing review for 7 additional days following vaccine administration using electronic capture and internet-based portal. If subject does not populate eDiary every 24-hours, the site will contact them for follow-up and document the contact in subject's source.
- 9 Sample collected if subject presents with AE requiring laboratory assessment.
- 10 If screening blood collection was greater than 28 days prior to Day 1 then laboratory assessments are to be repeated to establish baseline.
- 11 Serum at screening will be tested for HA immunology and will be considered baseline for the subject. A prescreen titer, collected under a separate site-specific protocol will be used to assess entry criteria.
- 12 PCR Test for Covid-19.
- 13 V01 sample to be tested by multiplex PCR test for abbreviated list of respiratory pathogens including Covid-19, Flu A, Flu B and RSV. Additional swabs may be collected at unscheduled visits, if the subject presents with respiratory symptoms that warrant additional testing; in such case a full respiratory panel is to be performed. 14 Collect, store, then batch test.
- 15 RNA analyzed for gene expression (no genetic testing of inherited diseases will be done)

Table 3: Schedule of Events – QIV Administration

Study Visit Number	V04 ¹	V05
Study Day Post-QIV Dose	Day 1	Day 29 ±7
Safety check	X^2	
Limited physical exam ³	$X^{2,4}$	X
Vital signs (BP, HR & temp)	X^2	X
Nasal swab – immunogenicity	X^5	X
Serum collection (HAI, MN, NAI and ELISA)	X^2	X
Administer licensed influenza vaccine 6	X	
AEs/Con meds	χ^2	X
SAEs	X^2	X

AE=adverse events; BP=blood pressure; ELISA=enzyme-linked immunosorbent assay; HAI=hemagglutination inhibition; HR=heart rate; QIV= quadrivalent influenza vaccine; IP=investigational product;

MN=microneutralization; NAI=neuraminidase inhibition; PI=Principal Investigator; QIV=quadrivalent inactivated vaccine; SAE=serious adverse events; temp=temperature; term=termination; V=visit.

- 4 At approximately 15 min after dosing.
- 5 Sample collected for secretory IgA immune response by ELISA

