8.3.2. Adverse Events

Treatment-emergent AEs (local and systemic) will be summarized as N (%) with AEs, with related-AEs, and by worst severity.

Incidence of treatment-emergent adverse events (TEAEs) will be reported by MedDRA-coded system organ class (SOC), preferred term (PT), and maximum severity.

Incidence of most frequent TEAEs and most frequent treatment-related TEAEs will be reported by SOC and PT

Listings of subjects who died, discontinued the study due to an AE, or experienced an SAE will be provided.

Dose-site reactions will be presented by reaction and severity.

Post-administration symptoms (eDiary) will be summarized by time point, worst occurrence, and days with symptoms.

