• At screening, prior to IP dose administration on Day 1, and on Day 8, a nasal swab will be collected. A PCR test for SAR-CoV-2 will be performed on the screening and Day 8 samples to assess eligibility. The Day 1 (V01) sample will be tested for an abbreviated set of respiratory agents. The Day 1 (V01) and Day 8 (V02) samples will be collected, combined in a shipment for the central lab and batch tested. The Day 1 (V01) sample will further be tested for the full respiratory pathogen panel using a multiplexed PCR assay if subject presents within 7 days of IP vaccination with symptoms of fever, upper respiratory illness, nephritis/cystitis, conjunctivitis or diarrhea.

a. To be assessed if total bilirubin is elevated above normal range.

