1.1. Statistical and Analytical Plans

1.1.1. Definitions and General Considerations for Data Analysis

- 1. This Statistical Analysis Plan (SAP) is based on Clinical Trial Protocol FluGen-H3N2-V002-V005 dated 10-May-2021 (v2.0).
- 2. All programming and calculations will be performed using SAS statistical software, version 9.4 or later.
- 3. Study Day 1 is the day of randomization and 1st IP administration; QIV administration is planned 28 Days after IP administration
- 4. Baseline (IP Baseline) is the last observation prior to IP administration, at the datapoint, not the record level. For example, for laboratory values, individual repeat tests values will be used for baseline when the entire panel may not have been repeated.
- 5. Summaries will be presented by treatment and age group and for all ages combined. Cohorts 2 and 3 will not be presented separately.
- 6. This study is not powered to detect differences in safety or immunogenicity between active and placebo groups. The sample size of 120 (80 active subjects and 40 placebo subjects) was chosen empirically based on studies of other vaccines in early-stage development.
- 7. There is no plan for test of hypotheses; p-values generated for immunogenicity are descriptive only and not adjusted for multiplicity.
- 8. For transparency and traceability, raw data, not results from calculations or corrections are to be transferred from external vendors. Differences between data transferred versus data as analyzed, will be documented in the CSR.
- 9. The clinical database will be locked prior to final analyses of immunogenicity assays. Details regarding these analyses may be included as amendments to this SAP.

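### SAP 9.2.1 records a pre-dose eDiary score, but the solicited-symptom tables do not use it, so unchanged pre-existing symptoms count as reactions in both arms

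*SAP*

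**What the plan says.** The first primary endpoint (Protocol 2.2.1) counts participants who "experience solicited local and systemic reactions during the 7 days after administration of investigational M2SR vaccine or placebo". It does not require the symptom to be new or worse than before dosing.

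SAP 9.2.1 states that temperature, seven systemic symptoms and two local reactions "were collected pre-dose and once daily for the 7 days following IP administration via a reactogenicity eDiary". The planned symptom summaries are the worst severity over the 7 days, and "the number of days with any grade of symptom (score > 0) will be summarized using frequencies and percentages". The pre-dose score has no stated use. Protocol 8.3.2 had planned slightly more: "Post-administration symptoms (eDiary) will be summarized by time point, worst occurrence, and days with symptoms". SAP 9.2.1 keeps a day-by-day summary for temperature only, and SAP 1 says that the SAP prevails where the two differ.

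The SAP does work with baselines elsewhere. SAP 1.1.1 has a general rule: "Baseline (IP Baseline) is the last observation prior to IP administration, at the datapoint, not the record level". SAP 9.4 reports vital signs as change from baseline and in shift tables, and SAP 9.2 limits treatment-emergent AEs by start date.

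The trial also takes nasal swabs around dosing. For V01, Table 2 of the protocol has: "V01 sample to be tested by multiplex PCR test for abbreviated list of respiratory pathogens including Covid-19, Flu A, Flu B and RSV". The V02 sample is tested for SARS-CoV-2 only. Appendix 3 adds: "The Day 1 (V01) and Day 8 (V02) samples will be collected, combined in a shipment for the central lab and batch tested". The SAP gives no listing, flag or analysis of these results.

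**The concern.** The solicited items are non-specific: runny or stuffy nose, cough, sore throat, headache, muscle aches, chills, reduced activity and reduced appetite. Several are on the protocol's own list of symptoms to be grouped as an upper respiratory infection (Protocol 6.2.3). Subjects are 50 to 85 years old, and Protocol 4.1 admits "Healthy adults and those with stable chronic conditions". Some can be expected to score above 0 on at least one item before they are dosed.

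For such a subject the planned tables cannot separate a lasting complaint from a reaction. The main result of a tolerability study in a new age group would then overstate how often symptoms follow dosing, in both arms, and would understate the contrast between arms if the vaccine does cause reactions. The data that would show this are, according to the SAP, already in hand.

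**Working it through.** The plan gives no figure on this point. Its only safety probability (Protocol 1.4: an AE of 20% prevalence, 15 subjects, over 95%) reproduces as 1 − 0.8^15 = 0.965. Nothing below depends on it.

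**Step 1: the rule applied to one diary.** Subject A scores a stuffy nose 1 before dosing and 1 on each of the 7 days. Subject B scores 0 before dosing and 1 on each of the 7 days. Under SAP 9.2.1 both have worst severity mild and 7 days with symptoms. A comparison with the pre-dose grade counts B and not A.

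**Step 2: model.** Let b be the share in each arm with a pre-dose symptom that persists unchanged, and p the new-onset rate (p0 placebo, p1 active). Assume that the two are independent, and that a reaction on top of an existing symptom raises its grade.

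- Rate as planned: 1 − (1 − b)(1 − p)
- Rate counting only new or worsened symptoms: p
- Arm difference as planned: (1 − b)(p1 − p0)

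The documents give none of b, p0 or p1. Assumed values: p0 = 15%, p1 = 30%, b = 5, 10 and 20%. Planned arm sizes are 80 and 40 (Protocol 3.2); the IPEVAL set used for these tables may be smaller.

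**Step 3: results.**

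| b | Active as planned | Placebo as planned | Difference (points) |
|---|---|---|---|
| 0 (same as new or worsened) | 30.0% | 15.0% | 15.0 |
| 5% | 1 − 0.95 × 0.70 = 33.5% | 1 − 0.95 × 0.85 = 19.25% | 14.25 |
| 10% | 1 − 0.90 × 0.70 = 37.0% | 1 − 0.90 × 0.85 = 23.5% | 13.5 |
| 20% | 1 − 0.80 × 0.70 = 44.0% | 1 − 0.80 × 0.85 = 32.0% | 12.0 |

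The active rate is 3.5 to 14 points too high, which is 2.8 to 11.2 of 80 subjects. The placebo rate is 4.3 to 17 points too high.

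**Step 4: no vaccine effect.** With 15% new onset in both arms, both planned rates read 19.3 to 32.0% and the expected difference is 0. The rule dilutes a true contrast; it does not create one.

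**Step 5: chance imbalance in b.** The standard deviation of the arm difference in b is √[b(1 − b)(1/n1 + 1/n0)].

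- 80 vs 40: 4.2 points at b = 5%, 7.7 points at b = 20%.
- 10 vs 5 (the 50-64 group, which SAP 1.1.1 presents separately): 11.9 points at b = 5%, 21.9 points at b = 20%.

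In the small group, an imbalance in pre-dose symptoms could by itself look like a vaccine effect or hide one. Without the pre-dose grades by arm, a reader could not tell.

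**The case against.** **Placebo already handles it.** Summaries are by treatment (SAP 1.1.1), and Protocol 3.6.3 gives placebo the role of measuring what occurs without active vaccination. This stands for direction: background symptoms enter both arms and add no expected excess to M2SR. A reader might infer that the tables present these symptoms as reactions to M2SR. They do not, because SAP 9.2.1 attributes no symptom to the vaccine. Placebo does not, however, undo the inflated absolute rates, the factor (1 − b), or a chance imbalance in a 10 vs 5 group.

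**The AE analysis judges causality and groups respiratory infections.** It does, but it does not feed these tables. Reporting a diary symptom as an AE was at the investigator's discretion, and SAP 9.2 says that the eDiary and AE data were not reconciled.

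**Entry criteria keep b low.** Protocol 4.2 excludes recent flu-like illness and Covid-19 exposure and has minor illness resolve before enrolment, and a limited examination precedes dosing. This is fair and is why the range for b stops at 20%. These rules address acute illness more than chronic nasal symptoms, headache or aches.

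**The tables show severity, not just any score above 0.** True, but an unchanged pre-dose grade is still carried into the worst-severity table.

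**The added table does not give a vaccine-attributable rate.** Correct. On the assumptions above, 15% of placebo subjects would still count. Only the contrast with placebo estimates that rate; the added table makes the contrast cleaner.

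**The swabs settle little.** This largely stands. V01 routinely covers four agents, V02 covers one, and the full panel is run only when symptoms prompt it. Confirmed SARS-CoV-2 requires withdrawal (Protocol 7.4). Withdrawal before the Day 29 sample removes the subject from IPEVAL, so that result is not wholly without effect, although the documents do not say when batch results return.

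**Conclusion.** The point holds as a gap in the analysis of the first primary endpoint that is cheap to close. Followed as written, SAP 9.2.1 counts unchanged pre-dose symptoms as solicited reactions in both arms. With b of 5 to 20% and new-onset rates of 15% and 30%, all assumed, the active rate reads 33.5 to 44% instead of 30%, and the difference falls from 15 to between 14.3 and 12.0 points. The effect is proportional to b and may be small.

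A reader might infer that the reported rate is about twice the attributable one or more. For example, a 20% vaccine-caused rate would read 1 − 0.80 × 0.80 = 36% at b = 20% and 1 − 0.60 × 0.80 = 52% at b = 40%, ratios of 1.8 and 2.6. That requires background shares for which the documents give no support, and no new-onset symptoms at all on placebo. With 15% new onset on placebo, the ratio of the planned to the new-or-worsened active rate is 33.5/30 = 1.1 to 44/30 = 1.5.

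No hypothesis test, power or sample-size figure is affected: the study is descriptive (SAP 10 and 11).

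**What to change.** Keep the planned tables. In SAP 9.2.1 add, for each symptom and for any local and any systemic symptom, n (%) with a maximum post-dose grade above the pre-dose grade, by arm and age group, with the pre-dose grade distribution beside it. For the any-symptom rows, count a subject if at least one component symptom is new or worsened. Show subjects without a pre-dose score in a separate row, in keeping with the SAP's rule against imputation. Add a footnote that a reaction no higher in grade than the pre-dose symptom is not counted; the planned table beside it covers that limit.

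As a minor supplement, list subjects PCR-positive at V01 or V02. If a sensitivity table is run, leave out only those positive on the pre-dose V01 sample. Excluding on the V02 result would condition a safety table on something measured after randomisation and dosing.

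The cost is a few tables and one listing, with no new data and no protocol change. One thing to confirm first: Protocol 6.2.4 describes diary entries only for the 7 days after dosing, so the fix relies on the SAP's statement that pre-dose scores were collected.
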